## Study Protocol and Statistical Analysis

### MATERIALS AND METHODS

This was an investigator-initiated double-blind randomized controlled trial approved by the Institutional Review Board at MetroHealth Medical Center in Cleveland, OH and registered with clinicaltrials.gov (CT03099863). We conducted and reported this study according to the consolidated standards of reporting trials guidelines for randomized controlled trials. An independent data safety monitoring committee oversaw this trial. We had no extra-institutional funding.

### DESIGN, SETTING, AND PARTICIPANTS

This study was performed between May 2016 and September 2019 at a single academic medical center. Adult women were eligible to participate if they were scheduled to undergo elective surgery by two female pelvic medicine and reconstructive surgery or minimally invasive gynecology surgery staff that would require intraoperative cystoscopy, including POP repair, mid-urethral sling placement (MUS), hysterectomy, and complicated excision of endometriosis. Cystoscopy is routinely performed with these procedures in our practice. Exclusion criteria included history of neurogenic bladder, recurrent UTIs, nephrolithiasis, congenital urogenital anomaly, allergy to neomycin or polymyxin, pregnancy, or surgery planned to include intradetrusor onabotulinumtoxin A injection, mesh excision, or fistula repair. Women were excluded if they were found to have a positive urine culture on routine preoperative testing, independent of symptoms, or from an intraoperative urine sample. All subjects provided written informed consent. Participation in this study did not have any direct benefit to individual subjects.

### INTERVENTION, RANDOMIZATION, AND BLINDING

Patients were randomized 1:1 at the time of surgery into two groups based on the type irrigation to be used with intraoperative cystoscopy: control (normal saline) or antibiotic (Neosporin G.U. [200,000 U polymyxin B sulfate +40 mg neomycin sulfate] in 1 L NS). The randomization scheme was assigned by a statistician using randomization software in blocks of 10. Allocation was concealed in an opaque envelope until the time of randomization. The patients and attending surgeon, who performed all evaluation and treatment of postoperative UTIs, remained blinded. Neosporin G.U. (Pfizer, 200,000 U polymyxin B sulfate 40 mg neomycin sulfate) is Food and Drug Administration approved for short-term use as a bladder irrigant to prevent bacteriuria associated with the use of indwelling catheters. The prepared solution is completely clear, bactericidal, and used as indicated, neomycin and polymyxin B are absorbed in clinically insignificant quantities. A neomycin or polymyxin solution was used in Hares' 1981 cystoscopy irrigation study, has been used successfully in spinal cord injury patients with bacteriuria, and is well tolerated. Additionally, the medication is inexpensive and readily available in our operating room pyxis.

## STUDY PROTOCOL

At the time of surgery, the randomization allocation envelope was opened by the surgical fellow. If indicated, this individual prepared the antibiotic solution by injecting 1 ml of neomycin or polymyxin into 1 L normal saline. The fellow remained independent of postoperative UTI diagnosis and treatment for study participants. The steps of the surgery remained standard; the study protocol made no alterations to usual care involving patient preparation, intravenous antibiotics, and instrumentation. We routinely use cefazolin for antibiotic prophylaxis for all surgeries, with the addition of metronidazole for hysterectomy in premenopausal patients, except in the case of associated allergies. Upon routine urinary catheter insertion, a urine sample was collected and sent for culture. Patients with a positive intraoperative urine culture were later excluded from analysis.

Intraoperative cystoscopy was performed in normal fashion with the previously designated bag of irrigation fluid. At the completion of cystoscopy, the bladder was drained as per standard operating procedure. To determine the volume of fluid used during cystoscopy, the fluid bag was weighed before surgery and again after cystoscopy. A foley catheter was replaced per surgeon discretion. Upon hospital discharge, standardized post-operative instructions were given to all patients, including signs and symptoms of infections or other concerning postoperative sequelae.

Postoperatively, patients were called at three time points (3 days, 2 weeks, and 4 weeks after surgery) to assess for urinary complaints and adverse events, including patient-reported diagnosis and treatment of UTI. Subjects were treated for postoperative UTI per attending surgeon discretion.

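### As written, the envelope is opened before the urine specimen that decides an exclusion is taken, so that specimen may be collected or missed with the arm known to a team member

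*Combined protocol and SAP*

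**What the plan says.** The STUDY PROTOCOL section tells the operation in sequence.

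- Allocation: "At the time of surgery, the randomization allocation envelope was opened by the surgical fellow".
- Preparation: "If indicated, this individual prepared the antibiotic solution by injecting 1 ml of neomycin or polymyxin into 1 L normal saline".
- Specimen: "Upon routine urinary catheter insertion, a urine sample was collected and sent for culture".
- Consequence: "Patients with a positive intraoperative urine culture were later excluded from analysis".
- Irrigation: "Intraoperative cystoscopy was performed in normal fashion with the previously designated bag of irrigation fluid".

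The DESIGN, SETTING, AND PARTICIPANTS section lists a positive culture from the intraoperative sample among the exclusion criteria. The INTERVENTION, RANDOMIZATION, AND BLINDING section places randomization at the time of surgery and says "Allocation was concealed in an opaque envelope until the time of randomization". It names the patients and the attending surgeon as blinded, and nobody else. The one safeguard stated for the fellow is separation from diagnosing and treating UTI in participants after surgery.

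**The concern.** An exclusion applied after randomization can be treated like a baseline criterion if two things hold: treatment cannot affect it, and its collection cannot depend on the arm. The first holds here, because the urine is drawn before irrigation. The second is not protected. In the order described, the fellow already knows the arm when the catheter goes in, and the fellow's safeguard does not extend to collecting or handling the specimen.

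The specimen decides who is analysed. If the care taken over it, or the chance that it is sent at all, differed by arm, the two analysed groups would no longer be the groups that randomization formed. The plan specifies no tabulation of missing or positive specimens by arm, so a difference of this kind could pass unseen.

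**Working it through.** The plan states no figure on this point, so the check is mainly a reading of the text, with a little arithmetic for scale.

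**1. Order of events.** The text runs: envelope opened, solution prepared if required, urine specimen at catheter insertion, cystoscopy with the allocated bag. No sentence times the envelope against the specimen; both the blinding section and the protocol section say only that allocation takes place at the time of surgery. The order therefore rests on the sequence of the account. Nothing contradicts it.

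**2. Who knows the arm.** The fellow opens the envelope and prepares the antibiotic, so the fellow knows the arm for every woman. The specimen collector is not named. The laboratory's blinding is not stated.

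**3. How the arm could affect the exclusion.**

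- *Treatment changing the culture.* Ruled out, because the specimen precedes irrigation.
- *More contamination in one arm.* This would wrongly remove women without true bacteriuria. If k such women, at the arm's average risk r, leave an arm of n, the rate becomes (rn − rk)/(n − k) = r. With the plan's 20.3% incidence, its 121 per arm and k = 5 for illustration: (24.563 − 1.015)/116 = 23.548/116 = 20.3%. On that assumption the rate does not move and only numbers are lost. A shift needs the removed women to differ in UTI risk, and the documents give no figure for that.
- *More missed specimens in one arm.* A woman without a specimen has no positive result, so she would presumably stay in the analysis; the plan does not say. With m missed specimens and culture positivity q, about m × q women who should have been excluded remain. Positivity is not given. At an assumed 10% to 20%, keeping five such women takes 5/0.20 = 25 to 5/0.10 = 50 missed specimens in one arm. That is 25/121 = 20.7% to 50/121 = 41.3% of it.

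**4. Room for exclusions.** The STATISTICAL ANALYSIS section allows for an estimated 30% lost to positive culture or to follow-up. By the plan's totals that is 242 − 186 = 56 women; 30% applied to 242 is 0.30 × 242 = 72.6. Either way the two causes are pooled, so the number of culture exclusions cannot be recovered.

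The opportunity for dependence on the arm is there on the text. Its effect on the UTI comparison cannot be sized from the documents, and the two routes that remain look weak.

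**The case against.** The strongest reply is that the specimen is hardly exposed to bias. It is taken as part of routine care, before any irrigant, and the exclusion turns on a culture result, not on anyone's judgement. The protocol says it changed nothing in preparation or instrumentation. Early opening creates an opportunity and no more, and since the envelope and the specimen are not timed against each other, even the opportunity is inferred. Preparing the bag early may also help keep the attending blinded. Most of this stands, and it is why the expected gain from a change is small. It does not remove the point: on the natural reading the arm is known first, and no safeguard covers the specimen.

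A reader might infer more than the documents support.

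- *That weighing proves the arm was fixed before the operation.* The text says "the fluid bag was weighed before surgery and again after cystoscopy". A bag of plain saline can be weighed before 1 ml is added to it, so early weighing does not show early allocation. A bag designated in advance means in advance of cystoscopy, not necessarily of catheterization.
- *That the catheter decision was made knowing the arm.* The text says "A foley catheter was replaced per surgeon discretion". The attending surgeon is stated to be blinded and the fellow is named separately, so the natural reading points to a blinded decision-maker. That decision also follows cystoscopy, so moving the envelope would not affect it.
- *That the fellow was operating or took the specimen.* The text says neither.

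**Conclusion.** The point holds as a modest design weakness. As the protocol is written, allocation is revealed to the fellow before the specimen that decides a post-randomization exclusion, and the fellow's separation from outcome assessment does not cover that step. This rests on three things: the account follows the order of events, the fellow is unblinded, and nothing unstated kept the fellow away from the specimen.

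It is a risk of bias, probably small, and the documents do not show that bias occurred. No percentage-point shift in the UTI rate should be attached to it. Such a figure would need the UTI risk of women wrongly removed or retained, and the documents do not give it. Nor is the exclusion invalid merely because the envelope may have been opened first; what matters is whether collection and culture were independent of the arm.

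**What to change.** For a trial still to be run to this plan: take the specimen when the catheter is inserted, as already done, and open the envelope only after that. Prepare the solution out of the blinded attending's view. The irrigant is first used at cystoscopy, which comes later. Weighing before surgery can stay, since 1 ml in 1 L is 1/1000 = 0.1% of the volume. No extra procedure is needed. The small downside is that the bag is prepared during the case, so the fellow has to be free at that moment.

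For this study, reported as performed between May 2016 and September 2019, the order can no longer be changed. The report should:

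- state when the envelope was opened relative to the specimen, and who collected the specimen;
- give the numbers of missing and of positive specimens by arm, separately from loss to follow-up;
- if the envelope did come first, note that order as a limitation.

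The cost is a short table and a few sentences, provided that the specimen records and the order of events can be recovered.

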## OUTCOME MEASUREMENTS

The primary outcome was the rate of postoperative UTI within 6 weeks after surgery. The Center for Disease Control and Prevention's definition of a symptomatic UTI was adapted to include the following: (1) at least one sign or symptom accompanied by positive urine culture with  $\geq 105$  colony-forming units/ml, (2) symptomatic UTI with clinician decision to treat as reported by the patient, or (3) at least one sign or symptom with positive urine dipstick (UA). Timing of diagnosis was recorded as either the date of the positive urine culture or the timing of the postoperative phone call when the patient reported treatment of a UTI (3 days, 2 weeks, or 4 weeks after surgery). A sensitivity analysis was performed of UTIs treated within 2 weeks of surgery and any adverse effects related to the use of antibiotic irrigation. We also evaluated outcomes in the subgroup who had a vaginal prolapse repair procedure, which was previously reported to be at highest risk for postoperative UTI.

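### Only the antibiotic bag is described as being injected at surgery, and no matching or masked step is given for saline bags, so preparation could reveal the arm to the attending who evaluates and treats UTIs

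*Combined protocol and SAP*

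**What the plan says.** All references are to the combined protocol and SAP.

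- **Who learns the allocation, and when** (Study Protocol): "At the time of surgery, the randomization allocation envelope was opened by the surgical fellow".
- **What is then done** (Study Protocol): "If indicated, this individual prepared the antibiotic solution by injecting 1 ml" of drug into the 1 L saline bag. No counterpart is given for the other arm.
- **The arms** (Intervention, Randomization, and Blinding): "control (normal saline) or antibiotic (Neosporin G.U".) in saline. The control is plain saline, with no sham additive mentioned.
- **Where the drug is kept** (same section): "the medication is inexpensive and readily available in our operating room pyxis".
- **Blinding** (same section): "The patients and attending surgeon, who performed all evaluation and treatment of postoperative UTIs, remained blinded".
- **Appearance** (same section): "The prepared solution is completely clear, bactericidal".
- **Separation of the fellow** (Study Protocol): the fellow takes no part in diagnosing or treating UTIs after surgery.
- **Treatment rule** (Study Protocol): treatment of a postoperative UTI is left to the attending's discretion.
- **Outcome** (Outcome Measurements): there are three routes into the primary outcome. The first is a sign or symptom with a positive culture, and the third is a sign or symptom with a positive dipstick. The second is "symptomatic UTI with clinician decision to treat as reported by the patient".

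**The concern.** As written, the two arms differ in an act that can be observed: drug is injected into the bag for some patients and not for others, on the day of surgery, by someone on the surgical team. A clear solution hides the arm once the bag is made, but it does not hide the making.

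This matters because of who might see it. The attending evaluates and treats every postoperative UTI, and under the second criterion a treatment decision in a symptomatic patient can create a primary-outcome event without a culture or dipstick. If the attending knew the arm, the threshold for treating doubtful symptoms could differ between arms. The difference in UTI rates would then partly reflect that threshold instead of the irrigant.

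**Working it through.** The plan states no figure on this point, so the check is mainly a comparison of its own statements.

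**1. Does the plan describe a difference in handling between arms?** Yes. The injection is conditional on allocation, and the control is defined as saline alone. The document mentions no sham injection, centrally prepared bags, bag cover, preparation out of sight or test of blinding.

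**2. Does any stated safeguard cover the preparation step?**

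| Safeguard stated | What it protects | Covers preparation? |
|---|---|---|
| Opaque envelope | Allocation before randomization | No |
| Clear solution | Appearance of the finished bag | No |
| Fellow kept out of UTI care | Fellow's influence on outcomes | No |
| Statement that the attending stayed blinded | Asserts the result | Gives no procedure |

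The bag was weighed before surgery, and cystoscopy used a bag designated beforehand. Both fit preparation away from the attending, but neither establishes it.

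**3. Can the attending's belief reach the primary outcome?** Partly.
- Criterion 2 depends directly on a decision to treat, although it also needs a symptomatic patient and is captured by patient report.
- Criteria 1 and 3 need no treatment decision. However, no scheduled postoperative culture is described, so whether a test is done may depend on the evaluation.
- The document does not say who made the final endpoint classification.

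**4. Would the planned sensitivity analysis detect the problem?** No. It restricts attention to UTIs treated within 2 weeks, so it changes the time window and still rests on treatment.

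**5. Can the size be calculated?** Suppose knowledge of the arm lowers treatment in the antibiotic arm. The spurious difference would then be

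rate × s × e × d × u

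- s: share of UTIs counted only through the decision to treat
- e: fraction of those that are equivocal
- d: relative drop in treating equivocal cases when the arm is known
- u: share of cases in which the arm becomes known

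Only the rate, 20.3% (Statistical Analysis section), is in the document. The other values below are assumptions:

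| s | e | d | u | Difference (percentage points) |
|---|---|---|---|---|
| any | any | any | 0 | 0 |
| 0.25 | 0.5 | 0.10 | 1 | 20.3 × 0.25 × 0.5 × 0.10 = 0.25 |
| 0.25 | 1 | 0.10 | 1 | 20.3 × 0.25 × 0.10 = 0.5 |
| 0.75 | 0.5 | 0.30 | 1 | 20.3 × 0.75 × 0.5 × 0.30 = 2.3 |
| 0.75 | 1 | 0.30 | 1 | 20.3 × 0.75 × 0.30 = 4.6 |

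The results run from nothing to several points, driven entirely by inputs the document does not supply. The sign is also assumed. The table shows which facts are missing and does not estimate a bias.

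**The case against.** The strongest reply is that the document states plainly that the attending remained blinded, and nothing in it contradicts this. It is a short methods text in the past tense, so a masking step that goes unmentioned is only weak evidence that there was none. The fellow was deliberately separated from UTI care, the solution was clear, and the bag may have been prepared out of sight. Two of the three outcome routes need a laboratory or dipstick result, and the other is reported by patients who were themselves blinded.

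Most of this stands, and it limits the point to a risk and a gap in description. Three stronger readings are tempting, but the document does not support them:

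- **That the attending was unblinded.** The document does not say where the bag was prepared or who was present. It says the drug was available in the operating-room cabinet, not that it was taken out in the attending's view. That the saline bag was left untouched is likewise an inference from silence.
- **That the attending alone decides which UTIs count.** Criteria 1 and 3 require no decision to treat, and the final classifier is not named.
- **That the bias could reach 4.6 points, or 45% of the 10.15-point difference that a halving of 20.3% would give (4.6 / 10.15).** That needs every criterion-2 case to be equivocal, the highest assumed share and drop, and an attending unblinded in every case. It also ignores untreated patients who would still count through a positive culture or dipstick.

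The reply does not remove the core of the point. None of the stated safeguards addresses an act performed in one arm only, and the assertion of blinding comes with no procedure for that step.

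**Conclusion.** The point holds as a risk to the double-blind claim. As described, preparation differs by arm at the time of surgery, and no step is given that would keep it from the attending. The attending's discretionary decision to treat is one of three routes into the primary outcome. The document does not show that unblinding occurred, and it says the opposite. Neither the size nor the direction of any bias can be derived from it.

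The conclusion rests on two readings: that the text describes the whole preparation procedure, and that the attending could have been in a position to see it. If bags were prepared out of the attending's sight, or saline bags were handled in the same way, a sentence saying so would largely settle the matter.

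**What to change.** **For a repeat or extension.** Make the act identical in both arms. For every participant the fellow injects 1 ml into the 1 L bag, study drug or normal saline according to allocation, out of the attending's sight. Bags carry identical labels showing only the study number. The cost is a syringe of saline and a short extra step per control case. The composition of the active solution is unchanged.

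**For the data already collected** (the study ran from May 2016 to September 2019, so the procedure itself cannot be altered):

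1. State where and in whose presence bags were prepared, and whether saline bags had any matching step or masking.
2. Add a sensitivity analysis of culture-confirmed UTIs (criterion 1) by arm, since a culture result depends less on the attending's belief than a decision to treat does.
3. If preparation was not masked, qualify the double-blind description.

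Items 1 and 3 cost a few sentences. Item 2 uses existing data but costs precision. With the planned 186 analysed patients, 93 per arm, a 20.3% rate gives only about 93 × 0.203 = 18.9 control-arm events over all criteria, and culture-confirmed events will be some part of that. It is also not fully protected, because the decision to send a culture may itself have been discretionary. It should therefore be read alongside the primary analysis and not replace it.

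### As described, an acute reaction to the irrigant reaches the trial data only if the woman knows of it and reports it by telephone on day 3 or later

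*Combined protocol and SAP*

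**What the plan says.** All references are to the combined protocol and SAP.

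- **Exposure (STUDY PROTOCOL).** "Intraoperative cystoscopy was performed in normal fashion with the previously designated bag of irrigation fluid". Then: "At the completion of cystoscopy, the bladder was drained as per standard operating procedure". Contact with the study solution is a single intraoperative episode.
- **Collection of adverse events (STUDY PROTOCOL).** "patients were called at three time points (3 days, 2 weeks, and 4 weeks after surgery) to assess for urinary complaints and adverse events". No start date or look-back period is given for the calls.
- **Planned analysis (OUTCOME MEASUREMENTS).** The plan analyses "any adverse effects related to the use of antibiotic irrigation". It gives no definition, grading, time window or data source.
- **Risk named in eligibility (DESIGN, SETTING, AND PARTICIPANTS).** "allergy to neomycin or polymyxin" is an exclusion, and the only one that names the components of the irrigant.
- **Rationale for low risk (INTERVENTION, RANDOMIZATION, AND BLINDING).** "used as indicated, neomycin and polymyxin B are absorbed in clinically insignificant quantities". The same section cites earlier use in a cystoscopy irrigation study and in spinal cord injury patients, and describes the solution as well tolerated.
- **Oversight (MATERIALS AND METHODS).** "An independent data safety monitoring committee oversaw this trial". The data it received are not described.

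**The concern.** The method of collection does not match the timing of the exposure. If the irrigant causes an immediate reaction, it will do so during the operation or in recovery, when the woman is anaesthetised or only just awake. The first described question about adverse events comes on day 3 and is put to her. She can report only what she noticed or was told.

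Clinicians would probably notice and chart such a reaction, but no described step carries that record into the trial database. The plan nevertheless intends to say something about adverse effects of the irrigation. What is at stake is how much a statement that none occurred would be worth for the hours in which the named hypersensitivity risk is most likely to show itself.

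**Working it through.** The documents give no safety figure to reproduce, so the main check is a comparison of sections.

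**Step 1: timing.** Exposure begins and ends on day 0 (cystoscopy, then drainage). The first described adverse-event contact is on day 3. Between the two, the text mentions only discharge instructions, which inform patients but do not record events. STATISTICAL ANALYSIS names REDCap as the database but describes no operative or in-hospital adverse-event form.

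**Step 2: what the calls can pick up.** With no stated look-back limit, the day-3 call could elicit a reaction from day 0 to day 3. It can do so only if the woman knew of the reaction and recalls it. The described method has no route for one she did not know of.

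**Step 3: who is counted.** STUDY PROTOCOL removes women with a positive intraoperative culture from the analysis. They had already been irrigated, so they belong in a safety denominator.

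**Step 4: what a count of zero would support.** Inputs from STATISTICAL ANALYSIS: 121 women planned per arm, and 186 in total before allowance for dropout, hence 186 / 2 = 93 per arm. With 0 events in n women and complete ascertainment, the one-sided 95% upper bound is 1 − 0.05^(1/n):

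- n = 121: 1 − 0.05^(1/121) = 0.0245, about 2.4%.
- n = 93: 1 − 0.05^(1/93) = 0.0317, about 3.2%.

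If each reaction is recorded with probability s, the recorded rate is s × p and the bound on the true rate p becomes 0.0245 / s. The documents give no value for s, so the range below is an assumption (n = 121):

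| s | Upper bound on true rate |
|---|---|
| 1.00 | 2.4% |
| 0.75 | 0.0245 / 0.75 = 3.3% |
| 0.50 | 0.0245 / 0.50 = 4.9% |
| 0.25 | 0.0245 / 0.25 = 9.8% |

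**Step 5: illustration with assumed reaction rates.** A 1% rate gives 121 × 0.01 = 1.2 expected reactions in the antibiotic arm; 3% gives 121 × 0.03 = 3.6. At 3%, the chance of recording none is 0.97^121 = 2.5% with complete capture, but (1 − 0.5 × 0.03)^121 = 0.985^121 = 16% with half captured. Neither rate comes from the documents.

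**The case against.** The strongest reply is that this reads much into silence. The text is a short, past-tense summary of a study run from 2016 to 2019. It does not say that the calls were the sole source. Operative-period data were plainly collected: irrigation bags were weighed, and surgical route and concurrent procedures were noted. The analysis of irrigation-related adverse effects is not tied to the calls. The allergy exclusion removes the women at most obvious risk. The intervention section's reassurance extends beyond the labelled use, since it cites prior cystoscopy use and good tolerability. The gap leaves the primary outcome untouched.

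Much of this stands. It lowers the expected rate of reactions and rules out three stronger readings that a reader might infer:

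- *No events from the exposure period are collected.* The calls have no stated look-back limit, so a known and remembered reaction could be reported.
- *The safety committee would see only recalled events.* The documents do not describe what it saw.
- *The tolerability rationale does not reach this setting.* The section cites earlier cystoscopy use.

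The mismatch remains. Low expected risk does not show how this trial would detect a reaction, and collecting operative measurements is not the same as collecting operative adverse events. The plan analyses adverse effects of the irrigation, and the one method it describes for finding adverse events begins three days after exposure ends.

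**Conclusion.** The concern holds in a limited form. The only adverse-event ascertainment described is patient report by telephone from day 3, for an exposure confined to surgery. Acute reactions enter the data by that route only if the woman was told of them or noticed them, and recalled them. A report of none would therefore be weak for the intraoperative and recovery period: the 2.4% bound for 0 of 121 assumes complete ascertainment, and the bound rises in inverse proportion to the fraction captured.

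This rests on reading the described method as the method used. It does not show that any reaction occurred or was missed. The capture fractions and reaction rates above are assumptions. The point bears on the credibility of a safety statement, not on the UTI comparison.

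**What to change.** In STUDY PROTOCOL, start adverse-event collection at the start of cystoscopy irrigation. From the existing operative, anaesthesia and recovery records, abstract intraoperative and recovery events, at least hypersensitivity reactions, into REDCap. Do this for every irrigated woman in both arms, including those later excluded for a positive intraoperative culture. Existing study staff should do the abstraction, not the fellow, who opened the allocation envelope. Report these events by arm together with the call data, and state the look-back period of each call.

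If such a review was already done, a sentence giving its source, time window and recorder settles the point.

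The cost is one REDCap form and added data entry for up to 242 women. No new visit, procedure or clinical rule is needed.
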